3.4.2.14. EULAR RESPONSE

Comparing a subject's DAS28 score (using CRP and ESR) relative to baseline allows to substantiate his/her improvement or response. The EULAR response criteria are defined in [Table 1 \[27\]](#).

The EULAR response will not be calculated on site but during the statistical analysis by the Biometrics-CRO.

Table 1: EULAR Response

Present DAS28	Improvement in DAS28 Relative to Baseline		
	> 1.2	> 0.6 and \leq 1.2	\leq 0.6
\leq 3.2	good response	moderate response	no response
>3.2 and \leq 5.1	moderate response	moderate response	no response
> 5.1	moderate response	no response	no response

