3.6.2. STATISTICAL AND ANALYTICAL PLAN

The statistical analysis plan (SAP) will be generated under responsibility of the Sponsor. The SAP will be finalized prior to database lock. Any deviation from the reporting and analysis plans will be reported in the section "Changes in the planned analysis" in the Clinical Study Report. Details of the data analyses will be specified in the SAP.

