#### **Efficacy endpoints:**

- American College of Rheumatology (ACR) ACR20, ACR50, and ACR70 response rate over time (Week 0, Week 12, Week 24, Week 36, Week 48, Week 60, Week 72, Week 84, Week 96 and Week 104).
- Actual values in ACR-N index improvement over time (Week 0, Week 12, Week 24, Week 36, Week 48, Week 60, Week 72, Week 84, Week 96 and Week 104).
- Actual values and change from baseline values in Disease Activity Score using 28 joint counts (DAS28) using CRP and ESR, simplified disease activity index (SDAI) and clinical disease activity index (CDAI) over time (Week 0, Week 12, Week 24, Week 36, Week 48, Week 60, Week 72, Week 84, Week 96 and Week 104).
- Disease activity: response rate of remission and response rate of low disease activity (LDA) based on DAS28(ESR), SDAI, CDAI, Boolean (only remission) over time (Week 0, Week 12, Week 24, Week 36, Week 48, Week 60, Week 72, Week 84, Week 96 and Week 104).
- Disease activity: response rate of DAS28(CRP) < 2.6 and response rate of low disease activity (LDA) based on DAS28(CRP) over time (Week 0, Week 12, Week 24, Week 36, Week 48, Week 60, Week 72, Week 84, Week 96 and Week 104).
- Disease activity: rate of maintained remission at consecutive time points based on DAS28(ESR), SDAI, CDAI, Boolean and rate of maintained LDA at consecutive time points based on DAS28(ESR) over time (Week 0, Week 12, Week 24, Week 36, Week 48, Week 60, Week 72, Week 84, Week 96 and Week 104).
- Disease activity: rate of maintained DAS28(CRP) < 2.6 at consecutive time points and rate of maintained LDA at consecutive time points based on DAS28(CRP) over time (Week 0, Week 12, Week 24, Week 36, Week 48, Week 60, Week 72, Week 84, Week 96 and Week 104).

- European league against rheumatism (EULAR) DAS28 response rate (good, moderate, or no response) over time (Week 0, Week 12, Week 24, Week 36, Week 48, Week 60, Week 72, Week 84, Week 96 and Week 104).
- Actual values and change from baseline values in HAQ-DI over time (Week 0, Week 12, Week 24, Week 36, Week 48, Week 60, Week 72, Week 84, Week 96 and Week 104).
- HAQ-DI response rate (i.e., those who have a clinically meaningful improvement from baseline of  $\geq 0.25$  in HAQ-DI) and HAQ-DI normal physical function response rate (i.e., those who have a score of  $\leq 0.5$ ) over time (Week 0, Week 12, Week 24, Week 36, Week 48, Week 60, Week 72, Week 84, Week 96 and Week 104).

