### 4.2 Key Definitions and Labels

#### 4.2.1 *Definition of baseline and change from baseline*

The baseline value will be the baseline value of the parent study.

The absolute change from baseline will be calculated for all post-baseline time points as:  
Change from baseline at time point t = value at time point t – baseline value

For selected efficacy endpoints, the percentage change from baseline will be calculated for all post-baseline time points as: Percentage change from baseline at time point t =  $100 * (value at time point t - baseline value) / baseline value$ . As percentage change can not be calculated for subjects with a baseline value of 0, these subjects will not be included for the corresponding summary analysis (if planned) and the respective column(s) will be kept blank for the corresponding listing.

For the changes from baseline, only subjects with both a baseline value and a value at the post-baseline time point will be included.

Wherever in the document 'change from baseline' is mentioned, it concerns the absolute change from baseline.

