- ACR20 response:
  - YES if ALL of the following criteria are fulfilled:
    - % improvement relative to baseline in tender/painful joint count  $\geq 20\%$
    - % improvement relative to baseline in swollen joint count  $\geq 20\%$
    - % improvement relative to baseline  $\geq 20\%$  for at least 3 of the following assessments: patient's assessment of pain, patient's global assessment of disease activity, physician's global assessment of disease activity, HAQ-DI, CRP
  - NO if not all of the above criteria are fulfilled
  - Handling of missing values:
    - if TJC or SJC are missing, ACR response will be missing
    - if any of patient's assessment of pain, patient's global assessment of disease activity, physician's global assessment of disease activity, HAQ-DI or CRP are missing, but at least 3 have a change from baseline  $\geq 20\%$  or at least 3 have a change from baseline  $< 20\%$ , ACR response can be derived, otherwise it will be missing.
- ACR50 response: definition similar to ACR20 response, but using 50% as cut-off
- ACR70 response: definition similar to ACR20 response, but using 70% as cut-off

- ACR-N index of improvement: minimum of the following 3 criteria:
  - % improvement relative to baseline in tender/painful joint count
  - % improvement relative to baseline in swollen joint count
  - Median % improvement relative to baseline of the following assessments: patient's assessment of pain, patient's global assessment of disease activity, physician's global assessment of disease activity, HAQ-DI, CRP
- $DAS28(ESR) = (0.56 \times \sqrt{TJC28}) + (0.28 \times \sqrt{SJC28}) + (0.70 \times \ln[ESR]) + (0.014 \times VASPA)$ , with VASPA measured in mm
- $DAS28(CRP) = (0.56 \times \sqrt{TJC28}) + (0.28 \times \sqrt{SJC28}) + (0.36 \times \ln[CRP + 1]) + (0.014 \times VASPA) + 0.96$ , with VASPA measured in mm and CRP in mg/L
- EULAR response is defined as follows based on the actual value of DAS28 (DAS28) in both ESR and CRP and the change from baseline in DAS28 ( $\Delta DAS28$ ) in both ESR and CRP:
  - Good response:  $\Delta DAS28 > 1.2 \text{ AND } DAS28 \leq 3.2$
  - Moderate response ( $\Delta DAS28 > 1.2 \text{ AND } DAS28 > 3.2$ ) OR ( $0.6 < \Delta DAS28 \leq 1.2 \text{ AND } DAS28 \leq 5.1$ )
  - No response ( $\Delta DAS28 \leq 0.6$ ) OR ( $0.6 < \Delta DAS28 \leq 1.2 \text{ AND } DAS28 > 5.1$ )
  - Pooled category Moderate+Good will be shown as well.

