- Disease activity is defined as follows based on the actual value of DAS28(ESR):
  - Remission:  $DAS28(ESR) < 2.6$
  - Low disease activity:  $2.6 \leq DAS28(ESR) \leq 3.2$
  - Moderate disease activity:  $3.2 < DAS28(ESR) \leq 5.1$
  - High disease activity:  $DAS28(ESR) > 5.1$
  - Pooled category Remission + Low disease activity will be shown as well
- Disease activity is defined as follows based on the actual value of DAS28(CRP):
  - $DAS28(CRP) < 2.6$
  - Low disease activity:  $2.6 \leq DAS28(CRP) \leq 3.2$
  - Moderate disease activity:  $3.2 < DAS28(CRP) \leq 5.1$
  - High disease activity:  $DAS28(CRP) > 5.1$
  - Pooled category  $DAS28(CRP) < 2.6$  + Low disease activity will be shown as well
- Boolean remission is defined as follows:
  - Yes:  $TJC28 \leq 1 \text{ AND } SJC28 \leq 1 \text{ AND } VASPA \leq 1 \text{ cm AND } CRP \leq 1 \text{ mg/dL}$
  - No: else
- Clinically meaningful improvement in HAQ-DI (clinically meaningful improvement from baseline – absolute change) is defined as follows:
  - Yes:  $\Delta HAQDI \geq 0.25$
  - No:  $\Delta HAQDI < 0.25$

- Normal physical function based on HAQ-DI is defined as follows:
  - Yes:  $HAQDI \leq 0.5$
  - No:  $HAQDI > 0.5$
- CDAI score = TJC28 + SJC28 + VASPA (cm) + VASPHA (cm)
- CDAI classification:
  - Remission:  $CDAI \leq 2.8$
  - Low disease activity:  $2.8 < CDAI \leq 10$
  - Moderate disease activity:  $10 < CDAI \leq 22$
  - High disease activity:  $22 < CDAI$
  - Pooled category Remission+Low disease activity will be shown as well
- SDAI score = TJC28 + SJC28 + VASPA (cm) + VASPHA (cm) + CRP (mg/dL)
- SDAI classification:
  - Remission:  $SDAI \leq 3.3$
  - Low disease activity:  $3.3 < SDAI \leq 11$
  - Moderate disease activity:  $11 < SDAI \leq 26$
  - High disease activity:  $26 < SDAI$
  - Pooled category Remission+Low disease activity will be shown as well
- Maintained remission at Week x: remission at Week x and all consecutive time points.

MTX and corticosteroid dose related endpoints will be derived as follows:

- MTX dose decrease from baseline at W0, W48 and W104:
  - Yes: daily dose at Week 0/ Week 48 / Week 104 visit < baseline dose
  - No: else
- Discontinuation of MTX dose at W0, W48 and W104:
  - Yes: daily dose at Week 0/ Week 48 / Week 104 visit = 0
  - No: else
- Change from baseline of MTX dose at Week 0/ Week 48 / Week 104
- Change from baseline of corticosteroid dose at Week 0/ Week 48 / Week 104

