**Table 14.2.1.6.2: HAQ-DI Score – Clinically meaningful improvement**

Frequency tabulation of the clinically meaningful improvement, based on the HAQ-DI score ( $\Delta HAQDI \geq 0.25$ ) at each time point, including a Wilson score 95% CI on the percentage of subjects with HAQ-DI response.

Population: ITO.

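### EULAR response in SAP 12.3 has the wrong sign: as written, every subject whose DAS28 improves is scored as a non-responder

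*SAP*

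**What the plan says.** **EULAR.** SAP 4.2.1 gives the formula "Change from baseline at time point t = value at time point t – baseline value" and adds that any mention of change from baseline in the document means this non-percentage change. SAP 12.3 defines EULAR response "based on the actual value of DAS28 (DAS28) in both ESR and CRP and the change from baseline in DAS28", written ΔDAS28, with these rules:

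- Good: Δ > 1.2 and DAS28 ≤ 3.2.
- Moderate: Δ > 1.2 with DAS28 > 3.2, or 0.6 < Δ ≤ 1.2 with DAS28 ≤ 5.1.
- No response: Δ ≤ 0.6, or 0.6 < Δ ≤ 1.2 with DAS28 > 5.1.

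Table 1 in protocol section 3.4.2.14 has the same cut-offs, but its columns are headed "Improvement in DAS28 Relative to Baseline". SAP section 11 lists four departures from the protocol; none concerns EULAR.

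**HAQ-DI.** SAP 12.3 introduces the responder rule with "Clinically meaningful improvement in HAQ-DI (clinically meaningful improvement from baseline – absolute change) is defined as follows" and sets ΔHAQDI ≥ 0.25 for a responder. The symbol ΔHAQDI is not defined. SAP 3.3 ("those who have a clinically meaningful improvement from baseline of" 0.25 or more) and Table 14.2.1.6.2 ("Frequency tabulation of the clinically meaningful improvement, based on the HAQ-DI score") both speak of improvement.

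**ACR missing components.** The ACR20 rule itself is written in percentage improvement. Its missing-data rule covers cases where components "are missing, but at least 3 have a change from baseline" on one side or the other of 20%.

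**Neutralizing antibodies (NAb).** In SAP Table 1 (section 9.1) the parent-trial column has Y in the negative row and N in the positive row. SAP 9.3.4 and the note to Figure 14.2.1.13.3 give Y as positive and N as negative. SAP 9.4.6 refers to Table 1 for NAb incidence over time.

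**The concern.** Lower DAS28 is better, so improvement gives a negative change under SAP 4.2.1. The EULAR rule in 12.3 rewards a positive change. Taken literally, it turns improvers into non-responders and some worsening subjects into responders.

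EULAR response is a listed efficacy endpoint in both documents. It feeds Table 14.2.1.2.2, Figure 14.2.1.2.2 and a column of Listing 16.2.3.3. The DAS28 change with the 4.2.1 sign is already needed for Table 14.2.1.2.1, so it is a natural variable to reuse. Under SAP 4.4 only ACR20 response is independently programmed; EULAR response gets review of output, code and log, and the specification behind that review is wrong.

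Both routes have a cost. Code that follows the SAP contradicts the protocol. Code that follows the protocol departs from the SAP, and protocol section 3.6.2 states: "Any deviation from the reporting and analysis plans will be reported in the section" of the study report reserved for changes to the planned analysis.

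**Working it through.** The documents give no figure to reproduce here. The EULAR result follows from the stated rules alone; the response rates further down rest on assumed inputs and serve only as illustration.

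**1. Improvers, by algebra.** Let b be the parent-trial baseline DAS28 and v the value at the visit. SAP 4.2.1 gives Δ = v − b. If v < b then Δ < 0, hence Δ ≤ 0.6, hence No response whatever v is.

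**2. Who could be Good as written.** Good needs v − b > 1.2 and v ≤ 3.2. So b < v − 1.2 ≤ 3.2 − 1.2 = 2.0. Only a subject with a baseline DAS28 below 2.0 could qualify, which is under the SAP's own DAS28(ESR) remission cut-off of 2.6, and only by getting worse.

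**3. Worked pairs.**

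| Baseline → visit | v − b | As written | Protocol Table 1 |
|---|---|---|---|
| 6.0 → 2.5 | −3.5 | No response | Good |
| 6.0 → 4.0 | −2.0 | No response | Moderate |
| 4.0 → 5.5 | +1.5 | Moderate | No response |
| 1.8 → 3.1 | +1.3 | Good | No response |

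**4. Enumeration.** All pairs in 0.1 steps, baseline 2.0–9.5 and visit 1.0–9.5. This checks the logic and does not forecast response rates.

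| Pairs | As written | With Δ = b − v |
|---|---|---|
| 3610 improving | 3610 No response | 1426 Good, 1521 Moderate, 663 No response |
| 2850 worsening | 2151 Moderate, 699 No response | 2850 No response |

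Reading the SAP's word absolute as magnitude, \|v − b\|, does not rescue the rule: the same 2151 worsening pairs stay Moderate.

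**5. Illustrative EULAR rates (assumed inputs).** Baseline and visit DAS28 taken as bivariate normal and integrated exactly. With baseline mean 6.0 (SD 0.8), visit mean 3.0 (SD 1.1) and correlation 0 to 0.6, Good is about 57% correctly coded and below 0.00001% as written; Good plus Moderate is 95.4–99.1% against at most 0.18%. Over baseline means 5.5–6.5 (SD 0.8), visit means 2.5–4.0 (SD 1.0–1.3) and the same correlations, Good is 20–76% against less than 0.001%, and Good plus Moderate is 70–100% against at most 4.7%.

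**6. HAQ-DI (assumed normal change v − b, mean m, SD s).** Improvement of at least 0.25: Φ((−0.25 − m)/s). Literal sign: 1 − Φ((0.25 − m)/s). At m = −0.5, s = 0.5 these are Φ(0.5) = 69% and 1 − Φ(1.5) = 7%. Over m from −0.3 to −0.7 and s from 0.4 to 0.6 they are 53–87% and 1–18%.

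**7. ACR missing-data rule.** Suppose one of the five components is missing, two of the other four improved by at least 20%, and none worsened by 20% or more. The missing component could make it three improved, so the intended result is missing. Read with the 4.2.1 sign, all four observed components have a change below 20%, so the response counts as derivable and becomes NO.

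**8. NAb at screening, baseline and Week 0.** SAP 9.1 requires these visits in by-timepoint outputs, and they carry only Y/N results. Let p be the share of samples positive for anti-drug antibodies and q the share of those that neutralize; SAP 9.2 imputes antibody-negative samples as NAb negative. The true rate is p·q; Table 1 coding gives p·(1 − q). At assumed p = 20%, q = 10% this is 2% against 18%. Over p = 10–40% and q = 5–50% it is 0.5–20% against 5–38%, and the two agree at q = 50%.

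**The case against.** The strongest reply is that the intended direction is recoverable and the exposure limited. The SAP rule reproduces the protocol's table cell by cell, that table is headed as improvement, and a Good response that requires DAS28 to rise is absurd on its face. The study is descriptive, with no primary or secondary endpoints and no inferential analyses. EULAR response is in neither sensitivity analysis nor the subgroup analysis, and the other disease-activity endpoints do not use it. A table with 0% Good would probably be noticed in review.

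Much of this stands. It shows a specification error, not wrong results. It does not make the text right: the SAP's EULAR wording never says improvement, the definition it relies on is explicit and applies throughout the document, and the nearby ACR20 rule shows the authors wrote improvement when they meant it. SAP 4.2.1 is itself sound; the defect is in 12.3.

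On the lesser items the reply carries more weight. The HAQ-DI heading gives the direction, so only the symbol needs defining. For NAb, 9.3.4 and the figure note are clear, and 9.4.6 names the response ratio, which belongs to the other column of Table 1. What remains is two transposed cells. The 9.3.4 note, however, covers only screening and baseline, not Week 0.

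**Conclusion.** The EULAR rule is wrong as written and must be corrected. This rests on no assumed data: any fall in DAS28 yields No response, and Good is reachable only from a baseline below 2.0. The consequence is confined to Table 14.2.1.2.2, Figure 14.2.1.2.2 and the EULAR column of Listing 16.2.3.3. Whether any output would in fact be wrong cannot be told from the documents.

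The other three items are wording corrections. HAQ-DI and the ACR missing-data rule state their purpose nearby but carry an undefined or misapplied term. The NAb transposition could reverse only the screening, baseline and Week 0 rows of Table 14.3.4.8; subject classes, the individual plots and post-baseline ratio results are unaffected. It is read from a table extracted from PDF, though its rows appear intact.

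**What to change.** - **SAP 12.3, EULAR:** define ΔDAS28 as baseline DAS28 minus DAS28 at time point t, in line with protocol section 3.4.2.14. Leave SAP 4.2.1 unchanged, because the change-from-baseline tables depend on it.
- **SAP 12.3 and Table 14.2.1.6.2, HAQ-DI:** define ΔHAQDI as baseline minus the value at time point t.
- **SAP 12.3, ACR missing-data rule:** state the 20% condition in terms of percentage improvement relative to baseline, as in the ACR20 rule.
- **SAP Table 1 (section 9.1):** swap the parent-trial NAb entries so that Y is positive and N negative, and state in 9.4.6 that this mapping applies at screening, baseline and Week 0.

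The cost is SAP wording plus a check of the derivation programs against the corrected signs, best done before database lock. No data collection or design change is needed.

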#### **4.2.2 *Presentation of treatment groups***

The following treatment group labels will be used in the tables, listings and figures, unless specified otherwise:

- ALX-0061 150 mg q2w + MTX (C201 PBO + MTX)
- ALX-0061 150 mg q2w + MTX (C201 75 mg q4w + MTX)
- ALX-0061 150 mg q2w + MTX (C201 150 mg q4w + MTX)
- ALX-0061 150 mg q2w + MTX (C201 150 mg q2w + MTX)
- ALX-0061 150 mg q2w + MTX (C201 225 mg q2w + MTX)
- ALX-0061 150 mg q2w + MTX (C201 all subjects)
- ALX-0061 150 mg q2w (C202 150 mg q4w)
- ALX-0061 150 mg q2w (C202 150 mg q2w)
- ALX-0061 150 mg q2w (C202 225 mg q2w)
- ALX-0061 150 mg q2w (C202 all subjects)
- All subjects

#### **4.2.3 *Totals over groups***

Grand total, pooling all subjects, will be displayed in all tables.

#### **4.2.4 *General presentation of results***

All results will be presented per treatment group, unless specified otherwise. All listings will be ordered by treatment group, subject, and time point, unless specified otherwise.

The analysis population will always be indicated in a subtitle in the table, listing or figure.

#### **4.2.5 *Visit Windows***

The visit windows as defined in Section 12.1 will be applied to all parameters.

### **4.3 General Methods**

#### **4.3.1 *Calculation of descriptive statistics***

Continuous variables will be summarized using descriptive statistics including the number of non-missing observations (n), the arithmetic mean, the standard deviation (SD) for general characteristics and for PK summaries or standard error (SE) for efficacy, safety and immunogenicity, the median, minimum and maximum.

Descriptive statistics of efficacy will additionally include a 95% confidence interval (CI) of the mean, calculated based on the large sample normal approximation. For changes from

baseline of efficacy parameters, the least squares (LS) mean and 95% CI derived from an ANCOVA model with treatment group as factor and baseline as covariate will be shown.

Descriptive statistics of PK concentrations will additionally include 5% and 95% percentiles, coefficient of variation (CV)% of arithmetic mean, geometric mean and geometric SD.

Descriptive statistics of continuous variables will be presented when  $n \geq 2$ . When  $n=1$ , only sample size (n) and mean are shown.

Categorical variables will be summarized using frequency counts and percentages. For efficacy, a Wilson score 95% CI on the percentage in each treatment group will also be shown. When count data are presented, the percentage will be suppressed when the count is zero. Missing values will not be included in the denominator count when computing percentages. For demographics and baseline disease characteristics a 'missing' row will be included to indicate the number of missing values, without percentages.

For the graphs showing mean values of continuous variables, an SE flag will be shown, while for graphs showing percentages, this will be the Wilson score asymptotic SE on the binomial proportions.

Calculated parameters will not be rounded in the derived datasets. The rounding will be done at the reporting level. Mean, median, 95% CI limits will be presented with one decimal more than data collected. Minimum and maximum will be reported with the same precision as data collected and SD and SE with two decimals more than data collected. Percentages will be tabulated with 1 decimal.

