## 6 EFFICACY

### 6.1 Main Efficacy Analysis

No inferential statistical analyses will be performed. All tables will be presented by treatment group and overall, including treatment groups defined by previous dosing regimen of the parent trial (cfr. section 4.2.2). All analyses will be run on the ITO. The main analysis will be on observed cases (OC).

Continuous efficacy endpoints will be summarized as follows:

- Actual values: descriptive statistics (mean, 95% CI on the mean [normal approximation], SE, median, minimum, and maximum) per endpoint and time point. The baseline value from the parent trial will be included to the summary, if applicable.
- Changes from baseline: baseline adjusted LS means and 95% CI from an ANCOVA model with treatment as factor and baseline as covariate, median, minimum and maximum per endpoint and post-baseline time point.

This will be done for the following parameters: ACR-N, DAS28(CRP), DAS28(ESR), SDAI, CDAI, HAQ-DI, SF-36 physical and mental component scores, FACIT-Fatigue, duration of morning stiffness, patient's assessment of pain (VAS-scale), patient's global assessment of disease activity (VAS-scale), physician's global assessment of disease activity (VAS-scale), CRP, ESR, TJC68, TJC28, SJC68, SJC28, MTX dose, corticosteroids dose. Different types of systemic corticosteroids will be converted to Prednisolone equivalent doses before calculating the cumulative dose of corticosteroids. The cumulative dose will be given in mg/day (Please refer to Appendix 2 section 16.2 for more details).

Categorical efficacy endpoints will be presented using a frequency tabulation of the parameter at each time point, including a Wilson score 95% CI on the percentage of subjects in the category of interest. The baseline value from the parent trial will be included to the summary, if applicable. This will be done for the following parameters: ACR20, ACR50, ACR70, EULAR response (including EULAR good response), DAS28(ESR) low disease activity / remission / maintained remission / maintained low disease activity, DAS28(CRP) low disease activity / DAS(CRP) < 2.6 / maintained DAS(CRP) < 2.6 / maintained low disease activity, SDAI low disease activity / remission / maintained remission, CDAI low disease activity / remission / maintained remission, Boolean remission / maintained remission, HAQ-DI clinically meaningful improvement, HAQ-DI normal physical function, MTX dose reduction rate, MTX discontinuation rate.

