All 95% CIs will be two-sided.

In addition, line plots of the mean actual values per time point, including SE bars, for continuous endpoints, and line plots of the response rates (in percentage) per time point, including SE bars, for categorical endpoints, will be provided.

Definitions and calculation of efficacy parameters are detailed in section 12.3.

A detailed list of tables, figures and listings can be found in section 13.2, section 14 and section 15.2, respectively.

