## 6.2 Other Efficacy Analyses

The sensitivity of results to missing data will be assessed by conducting a sensitivity analysis using LOCF imputed cases. Missing post-baseline values are imputed by the last non-missing preceding post-baseline value. Baseline itself is not imputed.

The sensitivity analysis will be done for the following efficacy endpoints:

- ACR20/50/70
- DAS28(ESR) actual values and changes from baseline
- DAS28(ESR) remission/low disease activity
- DAS28(CRP) actual values and changes from baseline
- DAS28(CRP) < 2.6/low disease activity

A second sensitivity analysis will be done using NRI imputed cases. Missing post-baseline ACR values are imputed with the value corresponding to that of non-responders.

This sensitivity analysis will be done for the following efficacy endpoints:

- ACR20/50/70
- DAS28(ESR) remission/low disease activity
- DAS28(CRP) < 2.6/low disease activity

In addition, for the same efficacy endpoints, a subgroup analysis will be conducted on the observed cases.

The following subgroups will be considered:

- Age category (<65 yrs at baseline, >= 65 yrs at baseline)
- Geographic region
- If any subcategory has less than 10% of the total number of patients then the subgroup analysis will not be produced.

A detailed list of tables can be found in section 13.2.

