**Table 14.2.5.2.1: DAS28 Score – Actual values and change from baseline by region**

Descriptive statistics of the DAS28(CRP) and the DAS28(ESR) score actual values and change from baseline at each time point by region.

Population: ITO.

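### Normal-quantile 95% CIs for raw efficacy means fall short of 95% in thin cells of the DAS28 age and region tables; whole parent arms are barely affected

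*SAP*

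**What the plan says.** SAP 4.3.1 sets the 95% CI of an efficacy mean as "calculated based on the large sample normal approximation". SAP 6.1 restates it: "Actual values: descriptive statistics (mean, 95% CI on the mean [normal approximation], SE, median, minimum, and maximum) per endpoint and time point". It adds: "All 95% CIs will be two-sided".

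The printing threshold is in SAP 4.3.1: "Descriptive statistics of continuous variables will be presented when" n is at least 2. At n = 1 only the count and the mean appear. No t quantile is mentioned, and the interval has no minimum n of its own.

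On layout, SAP 4.2.4 says: "All results will be presented per treatment group, unless specified otherwise". SAP 4.2.2 lists eight single parent arms (five from C201, three from C202), a pool for each study, and all subjects. Both the main analysis (6.1) and the subgroup analysis (6.2) use observed cases.

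The only suppression rule for subgroups is in SAP 6.2: "If any subcategory has less than 10% of the total number of patients then the subgroup analysis will not be produced". Two subgroup tables carry means of a continuous score. For region, Table 14.2.5.2.1 plans: "Descriptive statistics of the DAS28(CRP) and the DAS28(ESR) score actual values and change from baseline at each time point by region". Table 14.2.4.2.1 does the same by age category.

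Two other kinds of interval are specified differently. In the main tables, changes from baseline get LS means and CIs from an ANCOVA. Proportions get Wilson score intervals.

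**The concern.** A large-sample method is prescribed with no large-sample condition attached. When the SD is estimated from few observations, the normal quantile is too small a multiplier and the interval is too narrow.

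Thin cells are foreseeable from the plan itself. Data are split by parent arm, then by age or region, then by visit. Observed-case counts fall over two years, partly by design, because loss of joint-count response leads to discontinuation at the 12-weekly assessments. Geographic region sets Mexico alone against eleven European countries (SAP 5.3). The 10% rule looks at a subcategory's share of all patients, so it does not protect any single arm-by-visit cell.

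What is at stake is the reading of the tables. The study is descriptive, and consistency across arms, ages and regions will be judged from estimates and their intervals. An interval labelled 95% should be close to that where it is printed.

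**Working it through.** **Inputs.**
- Two-sided 95% level, normal quantile (SAP 4.3.1, 6.1).
- Statistics printed from n = 2 (SAP 4.3.1).
- Eight single parent arms (SAP 4.2.2).
- Up to about 501 subjects (SAP 3.2).
- 10% rule (SAP 6.2).

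Arm sizes, subgroup shares and retention are not given. An equal split over arms, the retention rates, enrolment below 501 and normally distributed data are therefore assumptions.

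**Nominal level.** z = 1.960 and 2Φ(1.960) − 1 = 0.950. The stated 95% is reproduced in the large-sample limit.

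**Actual coverage.** For normal data with estimated SD, mean ± 1.960·s/√n covers with probability 2·F(1.960; n−1) − 1, where F is the t distribution function on n−1 degrees of freedom. The last column is the t quantile divided by 1.960.

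| n | coverage with z | t quantile | widening with t |
|---|---|---|---|
| 2 | 70.0% | 12.71 | ×6.48 |
| 3 | 81.1% | 4.30 | ×2.20 |
| 4 | 85.5% | 3.18 | ×1.62 |
| 6 | 89.3% | 2.57 | ×1.31 |
| 10 | 91.8% | 2.26 | ×1.15 |
| 12 | 92.4% | 2.20 | ×1.12 |
| 31 | 94.1% | 2.04 | ×1.04 |
| 50 | 94.4% | 2.01 | ×1.03 |
| 63 | 94.6% | 2.00 | ×1.02 |

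A simulation of 200,000 normal samples gave 89.3% at n = 6, 91.8% at n = 10 and 94.6% at n = 63. Coverage first reaches 93% at n = 16 and 94% at n = 30.

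**Whole parent arms.**
- 501/8 = 62.6, about 63: 94.6%.
- At 50% retention, 31.3, about 31: 94.1%.
- With 300 enrolled and 50% retention, 300/8 × 0.5 = 18.8, about 19: about 93.4%.

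**Smallest subcategory that passes the 10% rule.**
- 0.10 × 501 = 50.1 subjects; 50.1/8 = 6.3, about 6 per arm at entry: 89.3%.
- At 50% retention, 3.1, about 3 per arm: 81.1%.
- With 300 enrolled, 30/8 = 3.75, about 4 per arm at entry: 85.5%. At 50% retention this is 1.9, about 2: 70.0%.

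**A larger subcategory.** At a 20% share of 501, 100.2/8 = 12.5, about 12 per arm at entry: 92.4%. At 50% retention, about 6: 89.3%.

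**Width.** At n = 6, 1.960/2.571 = 0.762, so the planned interval is 24% narrower than the t interval.

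**Skewness.** With an assumed lognormal variable (log-SD 1) at n = 6, coverage is 76.3% with z and 82.5% with t. The t quantile helps but does not restore 95%.

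**The case against.** The strongest reply is that little depends on these intervals. SAP 3.3 notes that the protocol defines no primary or secondary endpoints, SAP 6.1 rules out inferential analysis, and the sample size has no power basis. The n and SE stand beside each mean, so a reader can see a thin cell and compute a t interval. The pooled columns in the same tables are larger: at n = 50 coverage is 94.4%. All of this stands, and it limits the point to presentation.

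Three stronger readings are tempting, and the documents do not support them.

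- A reader might infer that results by parent arm are generally unreliable. The only size given, about 501 over eight arms, points to shortfalls of about half a point at entry and one point at 50% retention.
- A reader might infer that every efficacy interval is affected. Main-table changes from baseline use ANCOVA, and response rates use Wilson intervals; neither uses the normal approximation for a mean.
- A reader might infer that these intervals are the only measure of uncertainty shown. The SE is printed too, and the figures carry SE bars.

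It is also fair to say that the 6-per-arm cell is a scenario: a subcategory right at the cut-off, split equally. In addition, the two DAS28 subgroup table entries name neither a CI nor a split by treatment group. Both follow only from the general rules in SAP 4.2.4 and 4.3.1. Whether the changes from baseline in those tables would carry ANCOVA intervals is unclear, so the point is confined to actual values.

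**Conclusion.** The point holds within narrow limits. The SAP applies the normal quantile to raw efficacy means at any n from 2, and nothing in it keeps the resulting interval out of thin cells.

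In whole parent arms the loss is about 0.4 to 1.6 percentage points over the scenarios shown. The material shortfall is in the actual-value means of Tables 14.2.4.2.1 and 14.2.5.2.1. There a subcategory that just passes the 10% rule gives about 89% coverage per arm at entry and about 81% at 50% retention.

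These figures assume 501 subjects, an equal split over eight arms and normal data. Lower enrolment makes the cells thinner, and a larger subgroup share makes them less thin. No test or decision changes. What changes is whether the printed confidence level can be taken at face value.

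**What to change.** In SAP 4.3.1 and 6.1, replace the normal approximation with the t quantile on n−1 degrees of freedom for CIs of raw means only. State that CIs of ANCOVA LS means stay on the model's residual degrees of freedom. Wilson intervals need no change. An alternative is to suppress the CI of a mean below a stated n.

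The cost is a wording change in two SAP sections. Protocol 3.6.4 asks for a 95% CI with the mean but names no method, so it need not be amended.

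The downside is wider intervals: negligible in whole arms (×1.02 at n = 63), clear in thin cells (×1.31 at n = 6, ×2.20 at n = 3) and very large at n = 2 (×6.48). For markedly skewed variables, coverage in small cells will remain below 95%.
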